11.6 Monitoring Plan

This study will be monitored according to the Wilmot Cancer Institute's Data and Safety Monitoring Plan for Clinical Studies. The monitor must be allowed access to all protocol regulatory and source documents to assess compliance with the protocol, federal regulations, and good clinical practices. The monitor will assess data for completeness of source documents and confirm data being recorded in the EDC is accurate. For remote monitoring, the sites will provide source documents as required. The regulatory binder, patient cases, and drug accountability will be reviewed at monitoring visits.

11.7 Safety Analyses

The Data Safety Monitoring Committee (DSMC) at the Wilmot Cancer Institute, University of Rochester, provides oversight of study progress and safety by review of accrual and adverse events semi-annually or more if concerns arise. Any adverse events requiring expedited review per protocol will be submitted to the chair of this committee for determination as to whether further action is required. This committee will meet after 6 patients have been enrolled and received at least one cycle of therapy. If > 3 patients have delays in treatment administration due to toxicity, the protocol will be closed to accrual pending review and discussion with the principal investigators.

The safety coordinator will monitor adverse event rates utilizing the University of Rochester Cancer Center Clinical trial database. If the study has had two or more of the same SAE's reported in a month or more than six of the same SAEs in six months, the DSMC will review the summary of SAEs, discuss events with the study chair, and conduct a detailed review with the study chair. The DSMC will determine if further action is required. A copy of the DSMC report will be sent to all participating sites for review and submission to their local IRB.

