7.4 Criteria for Removal from Protocol Treatment

- Disease progression as defined by 1) PSA rise **with or without** radiographic evidence of disease progression or 2) the occurrence of a skeletal-related event (see section 6.0)
- Unacceptable toxicity very likely related to studydrugs
- Off study treatment for ≥ 30 days
- Initiation of new systemic treatment for PCa
- The patient may withdraw from the study at any time for any reason
- Death
- Product not available
- Lost to follow-up
- Decision by sponsor

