An adverse event, using the common terminology definition, is any unfavorable and unintended sign (including an abnormal laboratory finding), symptom or disease temporally associated with the use of medical treatment that may or may not be related to the treatment. Serious adverse event are defined as grade 3 and 4 toxicities that are believed to potentially impact the safety of the participant. Any patient with SAE that cannot be ameliorated with the use of adequate medical intervention should have their treatment interrupted until the toxicity improves to a Grade 2 or lower severity. Once toxicity improves, at the discretion of the treating physician the study combination can be re-started at a reduced dose (-1). Should the patient continue to have intolerable grade 2 or higher toxicity even at a reduced dose (-1), at the discretion of the treating physician the study combination can be further reduced to level -2. Patients with SAE or intolerable grade 2 toxicity Patients with SAE while on dose -2 will permanently discontinue study drug. The study coordinator should be notified of all SAE. Also if the study drug is delayed for more than 4 weeks for any reason or if a dose reduction of enzalutamide below 80 mg daily is required, patients will be removed from the protocol treatment.

Dutasteride/ finasteride is included in this regimen to potentially increase the efficacy of enzalutamide and to prolong the duration of response. Dutasteride is available only as 0.5 mg capsules. Finasteride is available only as 5 mg capsules. In the event grade 3 or grade 4 toxicity occurs and is known to be related to dutasteride or finasteride alone, 5 AR-inhibitor should be held permanently. In the event of an occurrence of a SAE that cannot be attributed directly to either enzalutamide or 5- AR inhibitor, the study combination should be held until toxicity improves to grade 2 or lower and treatment restarted at dose level -1.

For treatment or dose modification related questions, please contact [name] at [contact] or [name] at [contact]

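### The accrual-closing rule in section 11.7 names only treatment delays, so immediate stops, reductions without interruption and toxic deaths are not explicitly counted

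*Combined protocol and SAP*

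**What the plan says.** Section 11.7 schedules one early safety meeting: "This committee will meet after 6 patients have been enrolled and received at least one cycle of therapy". The rule attached to it is "If > 3 patients have delays in treatment administration due to toxicity, the protocol will be closed to accrual pending review". No unacceptable rate, error rates or reason for the threshold are given. No later use of the limit is stated for the planned 40 men, and accrual is not said to pause while the first 6 complete a cycle.

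The same section has other safeguards. The DSMC carries out "review of accrual and adverse events semi-annually or more if concerns arise", and its chair receives events that need expedited review. There are also two numerical SAE triggers, the second over a six-month window: "If the study has had two or more of the same SAE's reported in a month or more than six of the same SAEs in" that window. Either one leads to a detailed review, after which "The DSMC will determine if further action is required".

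Elsewhere the plan describes toxicity outcomes that the early rule does not name. Section 7.4 lists "Unacceptable toxicity very likely related to studydrugs" and, separately, death as reasons for removal from treatment. For grade 3 or 4 toxicity known to be due to the 5-AR inhibitor alone, section 12.0 says "5 AR-inhibitor should be held permanently". At the lowest dose level it says "Patients with SAE while on dose -2 will permanently discontinue study drug". Section 12.0 also requires dose modification for an intolerable Grade 2 event, with no prior interruption stated.

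**The concern.** A delay is a mild form of treatment-limiting toxicity: the man pauses and may resume. Read as written, a man who stops at once and never resumes has had no delay. Suppose that, of 6 men, 3 are interrupted and restart and 2 stop at once for toxicity. The count is 3 and accrual continues, although 3 + 2 = 5 of the 6 had treatment-limiting toxicity. If the 2 who stopped had only paused, the count would be 5 and accrual would close.

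This matters because of who is enrolled. Section 5.2.1 admits men judged not fit by geriatric assessment or at high risk of side effects from ADT. Section 1.3 says that the cited enzalutamide studies did not describe underlying health status, and that every man in the hormone-naïve study had ECOG performance status 0. Safety of the combination is a secondary objective (section 2.2). An early tripwire for this population should respond to the worst outcomes at least as readily as to the milder ones.

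**Working it through.** **Step 1. Which toxicity outcomes reach the count?**

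| Outcome | Where | Counted as a delay? |
|---|---|---|
| SAE that cannot be ameliorated: interruption, then possible restart at level -1 | 12.0 | Yes |
| SAE not attributable to one drug: combination held until improved | 12.0 | Yes |
| Removal after a toxicity-related delay of more than 4 weeks | 12.0 | Yes |
| Permanent hold of the 5-AR inhibitor | 12.0 | Undefined |
| Discontinuation at level -2 | 12.0 | Not in itself; usually yes through an earlier interruption |
| Modification for an intolerable Grade 2 event, no interruption stated | 12.0 | Not explicitly |
| Immediate removal for unacceptable toxicity | 7.4 | Not explicitly |
| Death | 7.4, 11.3 | Not explicitly; reaches the DSMC as an SAE |

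**Step 2. How often does the rule trigger?** The plan gives no operating characteristics, so there is no stated figure to reproduce. Read the rule as 4 or more of 6, with true rate p of counted events and q = 1 − p:

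P(trigger) = 15p⁴q² + 6p⁵q + p⁶

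At p = 0.5 this is (15 + 6 + 1)/64 = 22/64 = 0.344. At p = 0.6 it is 0.311 + 0.187 + 0.047 = 0.544 (rounded from unrounded terms).

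| True rate (assumed) | 20% | 30% | 40% | 50% | 60% | 70% |
|---|---|---|---|---|---|---|
| Triggers | 1.7% | 7.0% | 17.9% | 34.4% | 54.4% | 74.4% |
| Does not trigger | 98.3% | 93.0% | 82.1% | 65.6% | 45.6% | 25.6% |

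With 3 of 6 affected, accrual continues. The exact (Clopper-Pearson) 95% interval for 3/6 is 11.8% to 88.2%.

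**Step 3. What does partial counting cost?** Let c be the rate of all treatment-limiting toxicity, and assume that two thirds of it appears as a delay. The current rule then works at p = 2c/3, and a rule on the full composite at p = c. Both use the step 2 formula.

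| Composite rate c | Delay rate 2c/3 | Current rule | Composite count |
|---|---|---|---|
| 30% | 20.0% | 1.7% | 7.0% |
| 40% | 26.7% | 4.7% | 17.9% |
| 50% | 33.3% | 10.0% | 34.4% |
| 60% | 40.0% | 17.9% | 54.4% |

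The fraction is not in the documents. At c = 50%, if three quarters or one half appears as a delay (p = 0.375 or 0.25), the current rule triggers 14.6% or 3.8% of the time.

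**Step 4. The denominator.** The limit is a bare count, and more than 6 men may be on treatment by the meeting. With a count of more than 3 among n men, P(no trigger) = P(Binomial(n, 0.5) ≤ 3) at a true 50%: 65.6% for n = 6, 50.0% for 7, 36.3% for 8, 17.2% for 10 and 7.3% for 12. At a true 30%, the chance of triggering rises from 7.0% at n = 6 to 50.7% at n = 12. One sentence of the plan therefore describes very different rules.

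**Step 5. Optional repeated looks.** Apply a limit of more than half to the cumulative count at 6, 12, 20 and 30 men. These positions are assumed, because the plan gives no accrual rate. An exact recursion over the looks gives:

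| True rate | 30% | 40% | 50% | 60% |
|---|---|---|---|---|
| Single look at 6 | 7.0% | 17.9% | 34.4% | 54.4% |
| Looks at 6/12/20/30 | 9.4% | 29.5% | 62.8% | 90.2% |

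Looks at 6, 20 and 40 give 62.6% at 50% and 92.4% at 60%, so the gain does not depend much on timing.

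**The case against.** The strongest reply is that this rule is one part of a wider safety system. Three stronger readings are tempting, and the documents support none of them.

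- **That this is the only numerical tolerability rule.** It is not. Section 11.7 also has the two same-SAE triggers. Section 12.0 describes SAEs as grade 3 and 4 toxicities thought to affect safety, so those triggers can reach treatment-limiting toxicity. It is the only rule in these documents that closes accrual automatically. The institute's Data and Safety Monitoring Plan, cited in section 11.6, is not among them.
- **That men who stop, are reduced or die are never counted.** Step 1 shows that most SAE-driven reductions pass through an interruption and would count. A permanent hold might be read as a delay, and deaths reach the DSMC as SAEs.
- **That accrual would continue on no real evidence of tolerability, or that passing the look is clearance.** Nothing says so. The DSMC meets whatever the count, reviews adverse events twice a year, and can act at its discretion.

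It is also fair to say that the 50% and 60% benchmarks, the two-thirds fraction and the look positions are assumed, and that the primary analysis is unaffected.

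What remains is narrower. The SAE triggers need repeats of the same SAE. Intolerable Grade 2 toxicity need not be an SAE, and varied toxicities need not repeat. Semi-annual review has no stated limit on treatment-limiting toxicity. None of these safeguards corrects a count that can fall as outcomes get worse.

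**Conclusion.** The point holds in this form: the one automatic accrual-closing rule does not explicitly count immediate discontinuation, reduction without interruption, or toxic death. That follows from the wording and needs no assumed rate. The other safeguards narrow the gap but do not close it.

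The look is also weak early evidence. Read as 4 or more of 6, it triggers 34% of the time at a true 50% and 54% at 60%. Those figures rest on exactly 6 evaluable men and on assumed benchmarks; the sponsor's own threshold of more than half of 6 makes that range a reasonable test. Should more men be evaluable, the stated count triggers more often, and the plan does not say which case applies. The event definition should be corrected. Repeating the look is a choice for the sponsor.

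**What to change.** Amend section 11.7 in two ways:

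1. Count each man who has any of the following because of toxicity at least possibly related to either study drug: delay or interruption, dose reduction, permanent discontinuation of either drug, removal from treatment, or death.
2. Express the limit as more than half of the men evaluable at the look, and define evaluable.

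This takes a few sentences and uses data already collected. It changes the accrual rule only; the patient-level dose rules in section 12.0 are unchanged.

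The cost is more accrual pauses pending review, because the event is broader. If delays are two thirds of the composite, the chance at 6 men rises from 1.7% to 7.0% at a 30% composite rate, and from 4.7% to 17.9% at 40%. A proportion also triggers less often than a fixed count of more than 3 once 8 or more men are evaluable. The sponsor should choose that knowingly, or restrict the count to the first 6.

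Optionally, reapply the limit at the scheduled DSMC reviews. With the assumed looks at 6/12/20/30, detection rises to 63% at 50% and 90% at 60%. Pauses rise from 7.0% to 9.4% at a true 30% and from 17.9% to 29.5% at 40%, before allowing for the broader event.

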12.0 TOXICITY ASSESSMENT AND DOSE REDUCTION/DOSE ADJUSTMENT

All patients will be assessed for safety with frequent history and physical exams along with CGA at pre-specified intervals, and at Unscheduled Visits if necessary, including chemistries and hematology (see Section 8.0).

The study will utilize the CTCAE (NCI Common Terminology Criteria for Adverse Events) Version 4.0 for toxicity and Serious Adverse Event reporting. A copy of the CTCAE Version 4.0 can be downloaded from the CTEP home page (<http://ctep.cancer.gov>.) All appropriate treatment areas should have access to a copy of the CTCAE version 4.0 (appendix C)

General dose modification considerations

- Missed doses are to be omitted rather than made up
- If multiple toxicities are experienced, dose modification will be based on the toxicity requiring the largest dose reduction
- Reductions are based on the dose given in the preceding cycle and are based on toxicities observed since the prior toxicity evaluation
- Dose modifications are required for Grade 3 or Grade 4 adverse events (AEs) or intolerable Grade 2 AE that are considered at least possibly related to enzalutamide or dutasteride
- Toxicities will be assessed and reported as specified in the study calendar

- Dose levels are defined below

Dose Level	Enzalutamide	Dutasteride /Finasteride
0	160 mg daily	0.5/5 mg daily
-1	120 mg daily	0.5/5 mg daily
-2	80mg daily	0.5/5 mg daily

An adverse event, using the common terminology definition, is any unfavorable and unintended sign (including an abnormal laboratory finding), symptom or disease temporally associated with the use of medical treatment that may or may not be related to the treatment. Serious adverse event are defined as grade 3 and 4 toxicities that are believed to potentially impact the safety of the participant. Any patient with SAE that cannot be ameliorated with the use of adequate medical intervention should have their treatment interrupted until the toxicity improves to a Grade 2 or lower severity. Once toxicity improves, at the discretion of the treating physician the study combination can be re-started at a reduced dose (-1). Should the patient continue to have intolerable grade 2 or higher toxicity even at a reduced dose (-1), at the discretion of the treating physician the study combination can be further reduced to level -2. Patients with SAE or intolerable grade 2 toxicity Patients with SAE while on dose -2 will permanently discontinue study drug. The study coordinator should be notified of all SAE. Also if the study drug is delayed for more than 4 weeks for any reason or if a dose reduction of enzalutamide below 80 mg daily is required, patients will be removed from the protocol treatment.

Dutasteride/ finasteride is included in this regimen to potentially increase the efficacy of enzalutamide and to prolong the duration of response. Dutasteride is available only as 0.5 mg capsules. Finasteride is available only as 5 mg capsules. In the event grade 3 or grade 4 toxicity occurs and is known to be related to dutasteride or finasteride alone, 5 AR-inhibitor should be held permanently. In the event of an occurrence of a SAE that cannot be attributed directly to either enzalutamide or 5- AR inhibitor, the study combination should be held until toxicity improves to grade 2 or lower and treatment restarted at dose level -1.

For treatment or dose modification related questions, please contact [name] at [contact] or [name] at [contact]

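### The restart rule for an SAE of unclear cause names fixed level -1, so read literally it gives a man already on level -1 no enzalutamide reduction, in conflict with the section's own reduction rule

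*Combined protocol and SAP*

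**What the plan says.** Section 12.0 gives three dose levels. Enzalutamide is 160 mg at level 0, 120 mg at level -1 and 80 mg at level -2. The 5-AR inhibitor stays at 0.5 mg (dutasteride) or 5 mg (finasteride) throughout.

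The general considerations at the head of the section include "Reductions are based on the dose given in the preceding cycle". They also require a dose modification for grade 3 or 4 events, or intolerable grade 2 events, judged at least possibly related to enzalutamide or dutasteride.

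The text after the dose table sets out a sequence:

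- For this section, "Serious adverse event are defined as grade 3 and 4 toxicities" with a potential impact on the participant's safety.
- After an SAE that medical care cannot relieve, treatment is interrupted until grade 2 or lower. The physician may then restart at level -1, which the text calls a reduced dose.
- If intolerable grade 2 or higher toxicity continues at level -1, "at the discretion of the treating physician the study combination can be further reduced to level -2".
- "Patients with SAE while on dose -2 will permanently discontinue study drug".
- More generally, "if a dose reduction of enzalutamide below 80 mg daily is required, patients will be removed from the protocol treatment".

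A separate instruction covers an SAE that cannot be tied to one drug or the other: "the study combination should be held until toxicity improves to grade 2 or lower and treatment restarted at dose level -1".

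**The concern.** The last instruction names a destination level rather than a step. It works for a man at full dose, but for a man already reduced to 120 mg the named level is the dose on which the event occurred. A site that follows the sentence as written would hold treatment, wait for the event to settle, and restart him at that same dose, although the section provides a lower step before removal from treatment.

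The stake is re-dosing after a grade 3 or 4 event in older men who were enrolled because they were judged unfit by geriatric assessment or at high risk of side effects from ADT (section 5.2.1). Treatment runs until progression and may continue past week 97 (section 8.0), so an event on a reduced dose is plausible. Two sites apply the text (section 6.0) and could resolve the conflict differently.

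**Working it through.** The plan states no figure to reproduce. The check traces the unclear-cause sentence through the dose table for each level at which the SAE could begin, then compares the result with the other rules of section 12.0.

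Inputs (dose table, section 12.0): enzalutamide 160, 120 and 80 mg at levels 0, -1 and -2; 5-AR inhibitor 0.5/5 mg at all three.

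Formula: change on restart = (dose at onset − restart dose) / dose at onset.

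| Level at onset | Restart under the sentence alone | Change in enzalutamide | One level below onset | Other rule in section 12.0 |
|---|---|---|---|---|
| 0 | 160 to 120 mg | (160 − 120)/160 = 25% cut | 160 to 120 mg, 25% cut | Consistent |
| -1 | 120 to 120 mg | (120 − 120)/120 = 0% | 120 to 80 mg, (120 − 80)/120 = 33.3% cut | Preceding-cycle rule conflicts; step to -2 is discretionary |
| -2 | 80 to 120 mg | (80 − 120)/80 = −50%, an increase | None | Permanent stop governs |

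Row by row:

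1. **Level 0.** The sentence and the general rule agree.
2. **Level -1.** The general rule takes the preceding cycle's dose, 120 mg, as its reference. A restart at 120 mg is no reduction from that reference. The provision for moving to 80 mg says that the physician can reduce, not that he must, and it is worded for toxicity that continues on level -1. The unclear-cause sentence does not refer to it. No order of precedence is stated.
3. **Level -2.** The permanent stop after an SAE on this level is not limited by cause, so it settles the case. The sentence merely sits awkwardly beside it.

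The 5-AR inhibitor change is 0% between any two levels, so only the enzalutamide dose is in question.

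**The case against.** The strongest reply is that section 12.0 should be read as a whole. The general considerations come before every specific rule. The sequence from -1 to -2 to stop is not limited by cause, and a grade 3 or 4 SAE on 120 mg fits naturally under toxicity of grade 2 or higher despite a reduced dose. The unclear-cause sentence follows one about toxicity due to the 5-AR inhibitor alone, so its purpose may be to say that both drugs are held when attribution fails, after which the man joins the same sequence. The section also gives contacts for dosing questions, the DSMC reviews SAEs (sections 11.4 and 11.7), and sections 6.0 and 7.5 let the investigator stop treatment.

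Much of this stands. It shows that a restart at 120 mg is not the certain outcome, and that a careful physician has a written route to 80 mg or to stopping. It does not remove the conflict. The specific sentence is a directive, the route to 80 mg is optional, and the contacts, DSMC review and right to stop do not supply a restart dose.

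A reader might infer more than the text supports:

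- **That the rule raises the dose of a man on level -2 from 80 to 120 mg.** The permanent stop overrides it.
- **That leaving both drugs unchanged makes the defect worse.** The 5-AR inhibitor is never reduced by level, and it would be unchanged under any level-based fix.
- **That the sentence always breaches the mandatory-modification rule.** That rule covers events at least possibly related to enzalutamide or dutasteride. The documents do not equate an SAE of unclear cause with the Possible category of section 11.0, and some such events may be unrelated to either drug.

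**Conclusion.** The concern holds as an internal conflict confined to level -1. The unclear-cause sentence fits only an SAE at level 0. Taken literally it gives a man on level -1 a 0% enzalutamide reduction where one level down would be 33%, and the documents do not say whether this sentence or the preceding-cycle rule prevails.

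This is a minor safety-drafting correction. It does not touch power, alpha or any efficacy analysis. How often it would arise cannot be estimated, because the documents do not say how many men will reach level -1 or then have an SAE of unclear cause. Harm would also require the physician to use neither the discretionary step nor the right to stop. The point is still worth correcting because it concerns re-dosing after a grade 3 or 4 event.

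The conclusion rests on two readings: that the sentence carries no implied condition on the dose at onset, and that the stop at level -2 applies whatever the cause. Both follow the text as written.

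**What to change.** Replace the fixed level with a step. Suggested wording: *Hold both drugs until the event has fallen to grade 2 or below, then restart one dose level below the enzalutamide dose at onset (level 0 to -1; level -1 to -2). Patients on level -2 discontinue permanently.*

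This changes only the restart level. It keeps the restart as an instruction and leaves the discretionary step for continuing toxicity as it is.

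The cost is one sentence in a protocol amendment, with no extra patients, visits or procedures. The small downside is that some men on level -1 whose SAE was in fact unrelated to treatment would restart at 80 mg. The current rule already accepts the same trade for men on level 0, who drop to 120 mg.
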